Design: A Phase III, randomised, triple-blind, placebo-controlled, parallel-group multicentre trial of vitamin D3 supplementation. Overall, 323 (of the target of 865) children aged 1-5 years, with asthma triggered by URTI, ≥ 4 URTIs in past year (or ≥ 2 URTIs in past 12 months if pertaining to the pandemic period) and ≥ 1 OCS in the past 6 months (12 months since February 2022) were recruited in 9 or more Canadian centers over a 7-year period in this high-intensity 7-month protocol. Year-round, children were randomly assigned to one of the two following study arms: (1) Intervention—two oral boluses of 100,000 IU vitamin D3 (3.5 months apart) with 400 IU daily vitamin D3 or (2) Control—identical placebo boluses with daily placebo dose.

Research question: Can vitamin D3 supplementation decrease the number of asthma exacerbations per child requiring rescue OCS (predominantly physician-initiated) vs placebo?

Randomisation was implemented through the Applied Clinical Research Unit (ACRU), at the CHUSJ, under the direction of the study statistician, [name]. A computer-generated random list was utilized, with randomisation stratified by site to ensure balanced allocation across different locations. Children were allocated to either the vitamin D3 or placebo group in a 1:1 ratio using a permuted block randomisation method, which enhanced allocation concealment. Group allocation codes for each site were securely stored with restricted access by the Central Pharmacy (CHUSJ) and the independent biostatistician. The active vitamin D3 and placebo preparations, provided by the manufacturer Europharm, were identical in appearance and taste, ensuring blinding. The allocated treatment numbers were forwarded to site pharmacies, which prepared the bolus in coded syringes and the coded bottles containing the daily dose and dispensed the study drugs in masked kits to maintain the integrity of the randomisation process.

Analysis objectives

The primary objective of this analysis is to evaluate whether vitamin D3 supplementation leads to a 25% relative reduction in the mean number of exacerbations requiring oral corticosteroids (OCS) per child over a 7-month period compared to placebo. We hypothesized that the number of OCS per child would approximately follow a Poisson distribution.

The secondary objectives are to assess differences between the treatment groups in:

- Mean number and type of laboratory-confirmed respiratory infections during asthma exacerbations.

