Source documents anonymized and retained in the patient study binder include pharmacy records, medical records, relevant information from Dossier de Santé du Québec (DSQ) or similar databases if obtained by the treating physician, laboratory results, and pulmonary function test results.

The data is organized in a tabular format within REDCap, with each row representing a participant observation (one row per event per person) and each column representing a specific data field. Data exports are available in CSV, Excel, and XML formats. The data fields include various types such as text, number, date, and multiple choice. The data dictionary is accessible within the REDCap project and provides detailed descriptions of each data field, including field names, types and allowed values.

Samples and Laboratory Databases:

- Biobank log (xlsx file, managed by the study Coordination Centre)
- CHUSJ Lab results for urine and blood (xlsx file, uploaded directly to OwnCloud),
- McMaster University Lab results for nasal swabs (xlsx file, uploaded directly to OwnCloud),
- Oscillometry results (data exported from the Tremoflo software, managed by the study Coordination Centre)

The detailed description of samples/data transfer and storage is described in the Data Management Plan.

Analysis sets/Populations/Subgroups

The target population for this study includes children aged 1-5 years with physician-diagnosed asthma, who have experienced recurrent, moderate/severe viral-induced exacerbations in the

preceding year. These children were treated with daily or pre-emptive inhaled corticosteroids (ICS) alone or with adjunct therapy as the standard of care from randomization onwards, and were randomized to receive either vitamin D3 supplementation or placebo. The sampling frame consists of potentially eligible children seen in one of the 9 participating pediatric institutions. Recruitment occurred in the fall over 3 months (Sept to Nov) for 1 year (2018), over 5 months per year (from Sept to January) for 3 years (2019-2021), than year-round for another 3 years (2022-2024), over a total period of 7 years. The analysis sample (n=323) includes all randomized participants regardless of adherence to the intervention protocol or whether they completed the study (intention-to-treat analysis). Of note, the consent form allowed data collection of the primary outcome until 7 months post-randomization, even in case of withdrawals or loss to follow-up.

Inclusion criteria:

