The **ITT sample** includes all participants who are randomized into the study, regardless of whether they adhere to the study protocol or complete the study. The **per protocol sample** includes participants who adhered strictly to the study protocol without major deviations. This means they received the correct Study drug, swallowed more than 50% of Study Bolus, missed daily supplement intake for fewer than 40 days (or less than 20% of expected intake), did not experience unblinding of the study treatment and were eligible at randomization. For patients with a low daily Ca intake (< 350mg if aged 1-3 years; < 500 mg if aged 4-6 years), the bolus was administered only after receiving normal results for Ca, Ph, and ALP analyses. Additionally, there were no deviations impacting patient safety, rights, welfare, or data integrity.

The **complete case sample** includes all participants who completed the 7-month study period and provided the necessary data for primary and secondary endpoints. This includes participants who may have experienced major protocol deviations, such as incorrect study drug administration or missed daily supplements for up to 40 days, as well as minor deviations, such as delayed urine sample collections, as long as they did not withdraw from the study and their data is available for analysis.

Seven **subgroup analyses** were pre-specified at the start of the study as being of interest because of the potential for the relationship between vitamin D and asthma related outcomes to be modified by these characteristics. These include; Serum 25OHD Levels, ICS Therapy (Pre-emptive vs. Daily), Clinical Asthma Phenotype, Sex, Atopy, BMI category at baseline, Skin color according to the 6 category Fitzpatrick scale. An additional three variables were identified before analysis by group or unblinding, for exploration of subgroup effects. These include: Type 2 inflammation, OCS in the past 12 months, and step therapy using the GINA 2024 definitions.

Exposure(s), Endpoint(s) and Covariates

Exposure(s) of interest

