information on the coding and definitions for secondary outcome variables is provided in appendix 3. Each of these will be considered as binary variables separating participants into two groups for analysis as described below.

Planned subgroup analyses

In this study, seven baseline variables are *a priori* hypothesized to be potential effect modifiers:

- Baseline 25OHD serum level dichotomized (<75 vs. ≥ 75 nmol/L)
- Atopy (specific multiallergen IgE ≤ 0.35 or > 0.35 kUa/L),
- Asthma phenotype (viral-induced vs. multi-trigger),
- ICS therapy (pre-emptive vs. daily),
- Body mass index (< 85%ile vs. ≥ 85 %ile)
- Biological sex assigned at birth (male/female)
- Skin color (6 categories of Fitzpatrick scale, dichotomized for analysis as 1, 2 or 3 vs 4, 5 or 6)

Subgroups to consider (ad hoc)

Three additional variables were added to the set of potential subgroups to consider. These variables were added to the analysis plan prior to the start of analysis, in light of recent scientific knowledge since the beginning of the study

- Type 2 high vs. Type 2 low inflammation (Phadiatop ≥ 0.35 kUa/L) OR Eosinophils ≥ 300 cells/ μ L vs. neither)
- Past morbidity (≤ 2 vs > 2 OCS in past year)
- Prescribed GINA 4 Step-therapy at index visit (dichotomized as Step 1-2-3 vs 4)

Safety outcomes

The urine calcium:creatinine ratio, as a marker of normal calcium metabolism, was the primary safety outcome to assess the individual safety profile. Urine samples to test for hypercalciuria were systematically collected for immediate on-site analysis at baseline, 3.5 and 7 months, and at 10 days after each bolus. Site- and age-specific reference values were used for interpretation locally. In case of an elevated urine calcium:creatinine ratio, a site endocrinologist/bone specialist, blinded to group allocation, interpreted results and, if necessary, requested further analysis (urine or blood samples). Serious and non-serious adverse health events were ascertained at each visit and phone call.

The proportion of children with ≥ 1 occurrence of clinically significant:

- Hypercalciuria, clinically significant hypercalcemia (> 2.63 mmol/L), documented in the Safety Markers eCRF and Adverse effects eCRF; Q 3.3.1 Serum Ca Value (mmol/L) [safmark_biomark_caval].
- Elevated serum 25OHD (> 250 nmol/L—measured at the CHUSJ; exceptionally, if measured as part of investigation of adverse events, it may be documented in safety markers eCRF and

- Adverse effects eCRF;

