Positivity checks will be performed to verify the effectiveness of randomization and ensure that baseline characteristics are balanced across the study arms. The probability of intervention conditional on baseline variables will be calculated for all observations. These probabilities will be graphed to confirm that there are no violations of positivity. Should there be any violations, the statistician will investigate and characterize participants with a less than 5% or greater than 95% probability of intervention. The statistician will then notify the investigators and discuss whether a restriction of the analysis is necessary.

Descriptive analysis of serum vitamin D

Vitamin D values were measured at baseline, visit 2 and visit 3. Additional home visit measures were available for some participants. Vitamin D was assessed using Serum 25OHD testing at a central laboratory. These values will be summarized by study visit and intervention group.

Descriptive analysis of primary and secondary outcome measures:

Empirical distributions of primary and secondary outcomes will be generated overall and comparatively by intervention arm using graphical representations. Additionally, summary statistics, including measures of central tendency (e.g., mean) and variability (e.g., standard deviation), will be calculated and reported overall and by intervention arm for:

- The number of oral corticosteroids (OCS) courses per child
- The number of laboratory-confirmed viral upper respiratory tract infections (URTIs)
- Total number of viruses (all viruses included in all positive swabs) detected per child (this could include more than 1 virus identified in a given swab)
- Total number of swabs with at least 1 virus detected, thus number of 'positive' swabs per participant;
- At least one nasal swab detection of virus types in one of the following 10 viruses groups:
 - Rhino/Entero
 - InfluenzaA
 - InfluenzaB
 - Parainfl1
 - Parainfl2
 - Parainfl3
 - HMPV

- RSV
 - Adeno
 - SARSCoV2
- Mean number of ED visits with/without hospital admissions for asthma exacerbations per child over 7 months study period
- Proportion of children with intensification of preventive asthma therapy at visit 2, visit 3, or either.
- Mean duration of asthma symptoms per child reported verbally or documented on the validated written 'Asthma Flare-up Diary for Young Children' over the time frame of 7 months (with each means of recording considered as a separate outcome).

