- Mean duration of use of β 2-agonist was used during each cold/asthma flare-up reported verbally or documented on the validated written 'Asthma Flare-up Diary for Young Children' over the time frame of 7 months (with each means of recording considered as a separate outcome).
- Mean of out-of-pocket asthma related expenses per exacerbation
- The sum of the daily ADYC scores as a measure of the severity of asthma symptoms during exacerbations, completed daily by parents using the validated 17-item, each scored from 1 (best) to 7 (worst), Asthma Flare-Up Diary for Young Children symptoms (ADYC) and standardized over 7 days
- Mean intensity of β 2-agonist use reported on the diary as
 - Cumulative rescue bronchodilator use: \sum daily number of puffs from the first day until last day of use until last day of use, inclusively. Units [puffs/episode]
 - Average rescue bronchodilator score = Cumulative rescue bronchodilator use \div duration of use, units [average puffs/day]
- Mean parents' functional status during exacerbations per child
 - Reported as the mean ECAP score
 - Reported as Global functional status on a 7-point likert scale from 1-not at all, to 7-extremely

Primary Efficacy Analyses

A Poisson regression model, will be estimated, using an ITT approach, including only randomization group as a predictor and adjusting only for the stratification of randomization by clinical site. This model will be used to estimate the incidence rate ratio comparing the mean number of oral corticosteroids (OCS) per child during the 7-month follow-up by study group. If overdispersion is present, a negative binomial model will be used. If there are large variations in person-time an adjustment using an offset term will be made. Two sensitivity analysis are planned; 1) the incidence rate ratio will be stratified by the month of recruitment to explore the possibility of effect modification by seasonality and 2) the incidence rate ratio will be stratified by year of the pandemic (2000-2001) to assess the possibility of effect modification by exposure to the COVID-19 pandemic period. The original analysis plan included a fixed effect for each site. However, for sites with a very small number of recruited patients, these small sites may be grouped together.

Secondary outcome analyses

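### The COVID-19 sensitivity stratum is dated 2000-2001, when no child was recruited, and two loosely fixed rules (restriction after the positivity check, offset only if variation is large) need tightening

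*SAP*

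**What the plan says.** **Pandemic stratum.** The second sensitivity analysis in Primary Efficacy Analyses stratifies the incidence rate ratio by pandemic year and gives the years as 2000-2001. Analysis sets/Populations/Subgroups puts recruitment in autumn 2018, then September to January in the three seasons labelled 2019-2021, then year-round in 2022-2024. The inclusion criteria date the pandemic-related relaxation from the fall of 2020. The Design paragraph of the Introduction gives February 2022 for the 12-month OCS window.

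**Positivity check.** Under Description of study cohort and positivity checks, the purpose is stated as "Positivity checks will be performed to verify the effectiveness of randomization", and "The probability of intervention conditional on baseline variables will be calculated for all observations". Children below 5% or above 95% are characterised, and then "The statistician will then notify the investigators and discuss whether a restriction of the analysis is necessary". Elsewhere the SAP says "Children were allocated to either the vitamin D3 or placebo group in a 1:1 ratio using a permuted block randomisation method", with stratification by site. It also says "The analysis sample (n=323) includes all randomized participants regardless of adherence to the intervention protocol", that the ITT sample "includes all participants who are randomized into the study, regardless of whether they adhere to the study protocol or complete the study", and, for the primary model, "A Poisson regression model, will be estimated, using an ITT approach". None of these statements mentions the positivity check.

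**Offset.** Primary Efficacy Analyses adds a person-time offset only when variations in person-time are large, and does not define large. The Primary outcome section ends follow-up at the date of visit 3, or at 7 months from randomisation if visit 3 did not occur. Endpoint(s) places visit 3 at 7 ± 0.5 months.

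**The concern.** The years in the pandemic stratum are a wrong figure in a planned sensitivity analysis of the primary outcome. The right years cannot simply be read off the rest of the SAP, which dates pandemic-related changes in more than one way and gives no end to the period.

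The restriction step borrows a remedy from observational work, where some subjects may have had no real chance of receiving one treatment. In a 1:1 randomised trial that cannot arise by design. An extreme fitted value means sparse data, chance, or an error in randomisation conduct or data. Looking for such errors is sensible, but dropping the child repairs none of them. Because the probability is fitted from arm membership, any exclusion based on it is a post-randomisation exclusion. The SAP gives no criterion for the decision and no time point relative to seeing outcomes by arm. For the added subgroups, by contrast, it does fix the timing: "These variables were added to the analysis plan prior to the start of analysis".

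The conditional offset leaves a choice about the primary model to be made after the data are seen, on an undefined standard.

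**Working it through.** The SAP gives no figure of its own on these points, so there is nothing to reproduce. The checks below size each item.

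**1. Pandemic stratum.** Recruitment years are 2018-2024 and the stratum years are 2000-2001. The overlap is none, so 0 of 323 children fall in it. The assignment rule matters even with the years corrected. A child randomised in September 2019 is followed for 7 months, to April 2020, so randomisation date and follow-up period place that child in different calendar years.

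**2. How often the positivity rule flags a child.** Assume 162/161 children per arm (the nearest split to 1:1 for 323) and ignore block effects. A category of k children with its own model term is flagged if all k are in one arm:

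P = [C(162,k) + C(161,k)] / C(323,k)

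- k = 1: 100%
- k = 2: 161/323 = 49.8%
- k = 3: (161·160)/(323·322) = 24.8%
- k = 4: 12.3%
- k = 5: 6.1%

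A category with both arms present needs 1/k < 0.05, so at least 21 children split 20:1.

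Simulated allocation models agree:
- With 5, 10 or 20 common binary covariates (assumed prevalence 0.3), 0 of 400 trials per setting flagged anyone.
- In a second set (300 runs per setting, nine sites, assumed block size 4, nine common covariates), the flag rate was 0% with no rare level and either no site terms or equal sites. It was 100% with a one-child level. It was 47-52% with a two-child level, in the settings without unequal site terms.
- With site terms and assumed unequal sites (180, 60, 35, 20, 12, 8, 4, 2, 2), it was 54% with no rare level and 77% with a two-child level.

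Rare levels do exist in the data. The paragraph just before the positivity check lists ICS therapy among its key baseline characteristics. Appendix 3 reports 1 child without maintenance controller and 2 with pre-emptive therapy. Primary Efficacy Analyses expects some very small sites. Whether any of these enters the model is not stated.

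**3. Effect if a flagged child were dropped from the primary analysis.** Assume a true rate ratio of 0.75 and a control mean m of 0.6 to 1.5 courses. Let c be the courses of the dropped child.

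- Dropped from active: [(162·0.75m − c)/161] / m
- Dropped from control: 0.75m / [(161m − c)/160]

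Results (active; control):
- c = 0: 0.755; 0.745
- c = 4, m = 0.6: (72.9 − 4)/161/0.6 = 0.713; 0.45/[(96.6 − 4)/160] = 0.778
- c = 4, m = 1.5: 0.738; 0.758

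For scale, SE(log IRR) = √[1/(162·0.75m) + d/162 + 1/(161m) + d/161]. With dispersion d from 0.3 to 1.0 and m from 0.6 to 1.5 it lies between 0.116 and 0.191. The largest single-child shift above is |ln(0.713/0.75)| = 0.05. At m = 0.6 the SE is 0.167 to 0.191, so that shift is about 0.26 to 0.30 of one standard error.

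A child with 4 or more courses is itself rare. With m = 0.6 and d = 1, the probability is (0.6/1.6)⁴ = 2.0% in control and (0.45/1.45)⁴ = 0.9% in active.

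**4. Offset.** The visit 3 window is 6.5 to 7.5 months, or ±0.5/7 = ±7.1% of follow-up. In negative binomial simulations with equal follow-up between arms, the mean rate ratio was 0.740-0.753 both with and without log follow-up as an offset, and the SEs differed by at most 0.0001.

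**The case against.** The strongest reply concerns the positivity check. That section excludes nobody: it asks for investigation, notification and discussion. Three other statements define the analysis sample, the ITT set and the primary model on an all-randomised basis, and a reader may fairly hold that they prevail. A reader might infer from the restriction step that the plan abandons ITT or contradicts itself outright. The text does not support that. What stands is narrower: the restricted analysis is unnamed, and no sentence says which rule governs.

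It would also be too strong to say that no covariates are indicated. The preceding paragraph names ten baseline characteristics. That list is introduced as examples and is not tied to the probability model, so it is open rather than absent.

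On timing, the check uses no outcomes, and its symmetric threshold can be applied with coded arm labels, so it need not unblind anyone. It remains true that no time point is given.

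On the pandemic years, the same sentence names COVID-19, so nobody would actually run a stratum for the year 2000. This is probably a typing error. It still has to be corrected by the sponsor, together with the assignment rule.

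On the offset, a reader might infer that omitting it biases the rate ratio. That would require mean follow-up to differ between arms, and the documents show no such difference. The case for a fixed offset rests on removing a data-dependent choice.

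**Conclusion.** The point holds at minor to moderate weight. The pandemic years are wrong as written (0 of 323 children), and the rule assigning children to the stratum is missing. The restriction step has no remedial purpose under 1:1 randomisation and, if applied to the primary model, would conflict with the all-randomised definition. The SAP does not say that it would be so applied. A flag is improbable with common covariates. It becomes likely only if a very rare ICS level or an ungrouped tiny site enters the model, and dropping one child would probably move the rate ratio by well under one standard error. The conditional offset is a small, avoidable piece of discretion, and no bias figure can be claimed for it.

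The sizes rest on assumed arm totals, event means, dispersion, covariate prevalences, block size and site sizes. The SAP gives none of these beyond the total of 323 and the ICS counts.

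**What to change.** - **Pandemic stratum:** replace 2000-2001 with the intended years within the trial's recruitment and follow-up period. State whether randomisation date or follow-up period assigns a child.
- **Positivity check:** keep it, labelled as a descriptive check of randomisation conduct and data, and list its covariates. Add: *No randomised child is removed from the ITT analysis because of a fitted probability; any restricted analysis is a labelled sensitivity analysis fixed before outcomes by arm are seen.*
- **Offset:** include log(follow-up time) in the primary model in all cases and delete the condition on large variation. The planned adjustment for site only is unchanged.

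The cost is one corrected year range with its rule, one added sentence with a covariate list, and one deleted condition. No new data are needed, and an offset adds no parameter to estimate.
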